6.1.1 Randomization

Eligible patients will be randomized in a 1:1 ratio to either cenegegermin ophthalmic solution 20 mcg/mL TID or vehicle ophthalmic solution TID.

Randomization will be stratified by site to ensure balanced assignment across treatment groups. The stratified permuted block randomization list will be generated with a computer procedure by an independent statistician not involved in the conduct of the study.

Randomization will be performed through IRS. Each Patient Kit number will be randomly associated with a treatment group. The randomization list will be provided to the facility responsible for IMP packaging/labelling for the purpose of IMP preparation. Each randomized patient will be allocated with randomization number according to the stratified randomization list. Dropouts after randomization will not be replaced

The enrollment of patients will be scheduled in order to assure an inclusion of approximately 100 patients to ensure at least 90 patients assuming up to 10% of patients not evaluable after enrollment.

6.1.2 Unblinding

The identity of the treatments will remain unknown to the patient, investigator, site staff and Sponsor's clinical research personnel until the completion of the study (after full data base lock) except in case of specific events that will require unmasking of the patient.

The vials containing cenegegermin (20 mcg/mL) or vehicle will be identical in appearance, and the contents of the vials will be indistinguishable. All staff directly involved in the analysis of study results will remain masked to treatment assignments while the study is in progress.

The investigator will be provided with a protected access to the randomization list so only in case of a medical emergency the investigator can open the treatment allocation for a specific patient.

Also Dompé's Pharmacovigilance contact person will be provided with a protected access to randomization list, so if required by the Pharmacovigilance activities the Pharmacovigilance contact person can open the treatment allocation for a specific Patient.

In the event of a medical emergency where the knowledge of patient treatment is required to provide the patient with appropriate care, investigators will have the possibility to unmask the treatment assignment for a specific patient. The investigators are encouraged to contact the Contract Research Organization staff before becoming unmasked if there is sufficient time.

If the investigator becomes unmasked for any reason, this information will be recorded on source data and in the eCRF of the study, specifying the date and the reason.

Unmasking events will be recorded and reported in the final study report.

6.2 Overview of planned statistical analyses

Analyses will be conducted when all enrolled subjects have completed the study and the study database has been locked and unblinded. Key first efficacy results (KFR) will be provided close to the database closure in order to identify efficacy findings in a short timeframe.

The list of tables, listings, and figures to be provided at each analysis is reported in appendix 15.

7. Statistical Analysis

7.1 General

All patient data collected during the study will be listed by patient and site.

Appropriate descriptive statistics will be produced by treatment arms according to the nature of the variable.

For continuous data, number of observations, mean, standard deviation, median, range (minimum and maximum) and 95% confidence intervals will be presented.

For categorical data, frequency distributions and percentages with 95% confidence intervals (Wilson method) per category will be presented.

For primary analysis, the threshold for claiming statistical significance will 0.025 one-sided. For other analysis, unless otherwise specified, the significance level for statistical testing will be 0.05 and two-sided tests.

The statistical analyses (both descriptive and inferential) of some endpoints will be done on the eligible eye when applicable. Details will be provided in the statistical analysis outputs as notes.

Additional post-hoc analysis may be produced to further allow comparison between treatment and control, according to the results obtained. Any deviations from the original statistical plan (including unplanned analyses) will be documented in the CSR.

7.2 Analysis sets

7.2.1 Screened set

The Screened set will consist of all patients with signed written informed consent.

7.2.2 Enrolled set (ENR)

The ENR set will consist of all patients with signed written informed consent and fulfillment of eligibility criteria (i.e., not reported as screening failure).

7.2.3 Randomized set (RND)

The RND set will consist of all patients in the ENR set who are randomized to the study, regardless of whether they receive the IMP or not.

7.2.4 Full Analysis set (FAS)

The FAS population will consist of all randomized patients who received at least one dose of the investigational product. FAS population will be analyzed according to intention-to-treat (ITT) principle, i.e. by treatment allocation regardless happening of intercurrent events (treatment policy strategy). The FAS population will be used for the primary analysis of the study and to present results on efficacy data.

7.2.5 Safety set (SAF)

The SAF set will consist of all randomized patients who received at least one dose of the investigational product. SAF set will be analyzed according to the actual treatment received. The SAF population will be used to present results on safety data.

7.2.6 Per Protocol set (PP)

The PP set will consist of all randomized patients who received at least one dose of the investigational product and do not have Major Protocol Deviations. The PP population will be used for sensitivity analyses.

7.3 Primary estimand

The primary endpoints will be analyzed using treatment policy estimands, defined by the following:

Primary endpoint:

- Population: Subjects in the FAS population.
- Variable: Schirmer I test at week 4.
- Intercurrent event: The occurrence of an intercurrent event is irrelevant. All observed values will be used regardless of occurrence of an intercurrent event. Retrieved dropouts will be used for data imputation of missing data.
- Population-level summary: difference in proportion of patients reaching a value of Schirmer I test (without anesthesia) >10mm/5min at week 4.

Coprimary endpoint:

- Population: Subjects in the FAS population.
- Variable: SANDE global score at week 12.
- Intercurrent event: The occurrence of an intercurrent event is irrelevant. All observed values will be used regardless of occurrence of an intercurrent event. Retrieved dropouts will be used for data imputation of missing data.
- Population-level summary: difference in change from baseline in the global SANDE score at week 12.

7.4 Usage of analysis sets

The usage of the analysis sets for the creation of tables and figures is illustrated in Table 2. Unless otherwise specified, all listings will be done for RND set. All listings will report:

- planned and actual treatment names included,
- the flag(s) of the analysis set(s) used to analyze the information of the listing (according to Table 2).

Table 2: Usage of analysis set

Analysis	ENR	RND	FAS	SAF	PP
Subject enrolment and disposition	X				
Protocol deviations		X			
Study discontinuations		X			
Demographics and baseline characteristics			X		
Ocular and systemic Medical History and Concomitant Diseases			X		
Prior and concomitant medications			X	X	
Dry Eye History			X		
Other baseline characteristics			X		
Evaluation of Treatment Compliance and Exposure			X	X	
Evaluation of Efficacy			X		
Analysis of primary efficacy endpoint			X		
Sensitivity analyses			X		
Supportive analyses			X		X
Analysis of secondary efficacy endpoints			X		
Evaluation of Safety				X	

7.5 Sub-group analyses

Subgroup analyses of primary and secondary endpoints will be performed on the following subgroups of baseline characteristics:

- Age class (\leq Median, $>$ Median).
- Race.
- Ethnicity.
- Gender.

Within each subgroup level, descriptive in nature analyses will be performed on:

- Schirmer I test.

- SANDE global, frequency and severity scores.
- NEI scale.
- TFBUT.
- IDEEL questionnaire.

at each available timepoints by means of descriptive statistics.

In case of continuous measures, analyses will be provided for baseline visit, each post-baseline visit, and their change from baseline. Comparisons between treatments will be performed using two-sample t-test (assuming unequal variances) or, if the required assumptions are not met, the two-sample Mann–Whitney U test will be used. Assumption of normal distribution of endpoints for continuous data will be assessed by a visual inspection of distribution.

In case of categorical variables, the Fisher’s Exact test will be provided in addition to summary description.

Statistical tests for interaction (between subgroup variable and treatment arm) will be performed before investigating further subgroups: analyses of primary endpoints will be performed using regression models including treatment, subgroup variable and their interaction as covariate. If the interaction between subgroup variable and treatment arm is statistically significant at 15% nominal level in at least one regression model, then subgroup analysis will be performed. Variables that may be evaluated after test for interaction are:

Variables that may be evaluated after test for interaction are:

- Region (EU, US),
- Sjögren's syndrome (primary, secondary), *where “primary” is defined as a confirmed diagnosis of Sjögren's syndrome while “secondary” as other autoimmune disease known to induce Sjögren's Dry Eye Disease,*
- Medical history,
- Concomitant medication.

Subgroup levels may be pooled to have an adequate number of subjects per strata to perform the analysis. Decision on pooling will be taken during the Blind Data Review Meeting (BDRM), before data base lock.

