9.4.6. Subgroup analysis

Subgroup analyses of primary and secondary endpoints will be performed on the following subgroups of baseline characteristics:

- Age class (\leq Median, $>$ Median),
- Race,
- Ethnicity.

Statistical tests for interaction (between subgroup variable and treatment arm) will be performed before investigate further subgroups: analyses will be performed if interaction tests between treatment and variable is statistically significant at 15% nominal level. Variables that may be evaluated after test for interaction are:

- Region (EU, US),
- Sjögren's syndrome (primary, secondary),
- Medical history,
- Concomitant medication.

Statistical details and potential new subgroups definitions will be reported in the SAP.

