Table 14.2.5.4.3	Absolute values and change from baseline in IDEEL Dry eye Symptom bother module at each timepoint.	FAS	X	X
Table 14.2.5.5	Absolute values and change from baseline in Cornea and conjunctiva vital staining with fluorescein (NEI scale) at each timepoint.	FAS	X	X
Table 14.2.5.6	Absolute values and change from baseline in TFBUT at each timepoint.	FAS	X	X
Table 14.2.6.1.1	Subgroup evaluation: Schirmer I test (without anesthesia) >10mm/5min at week 4 - Treatment by region interaction. Logistic regression model - Multiple imputation	FAS		X
Table 14.2.6.1.2	Subgroup evaluation: Schirmer I test (without anesthesia) >10mm/5min at week 4 - Treatment by Sjögren's syndrome interaction. Logistic regression model - Multiple imputation	FAS		X
Table 14.2.6.1.3	Subgroup evaluation: Schirmer I test (without anesthesia) >10mm/5min at week 4 - Treatment by medical history interaction. Logistic regression model - Multiple imputation	FAS		X
Table 14.2.6.1.4	Subgroup evaluation: Schirmer I test (without anesthesia) >10mm/5min at week 4 - Treatment by concomitant medication interaction. Logistic regression model - Multiple imputation	FAS		X
Table 14.2.6.2.1	Subgroup evaluation: Change from baseline in the global SANDE score at week 12 - Treatment by region interaction. Analysis of Covariance (ANCOVA) - Multiple imputation	FAS		X
Table 14.2.6.2.2	Subgroup evaluation: Change from baseline in the global SANDE score at week 12 - Treatment by sjögren's syndrome interaction. Analysis of Covariance (ANCOVA) - Multiple imputation	FAS		X
Table 14.2.6.2.3	Subgroup evaluation: Change from baseline in the global SANDE score at week 12 - Treatment by medical history interaction. Analysis of Covariance (ANCOVA) - Multiple imputation	FAS		X
Table 14.2.6.2.4	Subgroup evaluation: Change from baseline in the global SANDE score at week 12 - Treatment by concomitant medication interaction. Analysis of Covariance (ANCOVA) - Multiple imputation	FAS		X
Table 14.2.6.3.1	Absolute values and change from baseline in Schirmer I test at each timepoint by age class.	FAS		X
Table 14.2.6.3.2	Absolute values and change from baseline in Schirmer I test at each timepoint by race.	FAS		X
Table 14.2.6.3.3	Absolute values and change from baseline in Schirmer I test at each timepoint by ethnicity.	FAS		X

Number	Title	Population	KFR	Final Analysis
Table 14.2.6.3.4	Absolute values and change from baseline in Schirmer I test at each timepoint by gender.	FAS		X

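### For age, race, ethnicity and gender the SAP plans a treatment test inside each level but no interaction and no presented treatment difference with CI, so a uniform effect will often look like a subgroup difference

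*SAP*

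**What the plan says.** SAP 7.5 sets up two tiers of subgroup.

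- **First tier: age class (split at the median), race, ethnicity and gender.** The protocol's subgroup section (9.4.6) says: "Subgroup analyses of primary and secondary endpoints will be performed on the following subgroups of baseline characteristics". SAP 7.5 opens in the same terms and adds gender to the protocol's list of three. It continues: "Within each subgroup level, descriptive in nature analyses will be performed on" Schirmer I, the SANDE scores, NEI, TFBUT and IDEEL, at each timepoint. For continuous measures, "Comparisons between treatments will be performed using two-sample t-test (assuming unequal variances"), with Mann-Whitney as fallback. For categorical variables, Fisher's "Exact test will be provided in addition to summary description".
- **Second tier: region, Sjögren's type, medical history and concomitant medication.** Here "Statistical tests for interaction (between subgroup variable and treatment arm) will be performed before investigating further subgroups". These are models of the primary endpoints. Subgroup results follow if the interaction is "statistically significant at 15% nominal level in at least one regression model".

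The output list in SAP 15.1 has the same structure. Tables 14.2.6.1.1-4 and 14.2.6.2.1-4 give interactions for the second-tier variables only. For the first tier, Schirmer appears in Tables 14.2.6.3.1-4, of which the first is titled "Absolute values and change from baseline in Schirmer I test at each timepoint by age class". No listed table gives responders above 10 mm/5 min by age class, race, ethnicity or gender.

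**The concern.** The purpose of a subgroup analysis here is to see whether the treatment effect is consistent. A significant result in one level and a non-significant one in the other does not test that. It mostly reflects how many patients each level holds. With about 90 evaluable patients, halving or quartering the sample costs so much power that mixed results are expected even when the effect is identical everywhere. A reader of the study report could then take a uniform effect to be confined to one age group or one sex.

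The second issue is a mismatch. The first co-primary is a responder proportion, and SAP 7.3 defines its summary measure as a difference in proportions. The subgroup text covers the primary endpoints, but the table list shows that Schirmer measurement by subgroup only in continuous form.

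**Working it through.** **Inputs.** SAP section 5 gives 1:1 randomization, 90 evaluable patients (45 per arm), vehicle responder rate 5% and a difference of 30 points (so 35% on cenegermin), a SANDE difference of 15 points with SD 20, and one-sided alpha 0.025. SAP 7.1 sets two-sided 0.05 for non-primary tests. The median age split gives 22 or 23 patients per arm per half. The documents give no level shares for race, ethnicity or gender, so the uneven splits below are assumptions.

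**The plan's own power figures.** Two proportions, 35% v 5%, 45 per arm, normal approximation: 95.8%. SANDE by noncentral t, with noncentrality 15 / (20 × √(2/45)) = 3.56: 94.0%. Product 0.958 × 0.940 = 0.90. All agree with section 5; the sample size is not in question.

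**Formula.** If the true effect is the same in both levels and the levels have powers *a* and *b*, the chance that exactly one is significant in favour of cenegermin is *a*(1 − *b*) + *b*(1 − *a*).

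**Age halves, SANDE.**
- 22 per arm: noncentrality 15 / (20 × √(2/22)) = 2.49, power 0.681.
- 23 per arm: noncentrality 2.54, power 0.701.
- Exactly one significant: 0.681 × 0.299 + 0.701 × 0.319 = 0.427. Both significant: 0.681 × 0.701 = 0.477.
- A simulation of 8,000 trials with the unequal-variance t-test and an even split gave 0.437.
- With a smaller true effect the figure is somewhat higher: 0.498 at 12.5 points and 0.469 at 10 points.

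**Age halves, Schirmer responder, two-sided Fisher by exact enumeration.** The result depends on how the odd patient falls.

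| Halves (cenegermin v vehicle) | Power in each | Exactly one significant |
|---|---|---|
| 22 v 22 and 23 v 23 | 0.651, 0.679 | 0.446 |
| 22 v 23 and 23 v 22 | 0.755, 0.691 | 0.402 |

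**Uneven levels, SANDE (assumed shares).**

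| Split | Power, larger level | Power, smaller level | Exactly one significant |
|---|---|---|---|
| 75/25 | 0.859 | 0.396 | 0.57 |
| 85/15 | 0.899 | 0.243 | 0.70 |

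**Interaction test for comparison.** In the same simulation, a treatment-by-subgroup test at 5% flagged the uniform effect in 5.0% to 5.4% of trials per factor.

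**Precision of that interaction.** With even halves, the SE of the difference between the two SANDE effects is 20 × √(4/22.5) = 8.4 points. Power against a 15-point interaction at two-sided 5% is about Φ(15/8.43 − 1.96) = Φ(−0.18) = 0.43.

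**The case against.** Four points can be made for the plan.

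1. **The analyses are labelled descriptive.** No claim rests on them. Neither the co-primary tests (SAP 10.1.1) nor the key secondary hierarchy (10.2.1) is touched, and the documents nowhere plan to contrast a significant level with a non-significant one. This stands, and it limits the consequence to misreading. It does not remove the p-values, which the same section explicitly plans.
2. **The plan gives more than p-values.** A reader might infer that the outputs cannot address consistency at all. That goes too far. SAP 7.1 specifies n, mean, SD and 95% CI for continuous data and percentages with Wilson intervals for categorical data. An unadjusted SANDE difference per level, and an interaction contrast, could be worked out from those. What is missing is a presented contrast, adjusted as in the primary analysis.
3. **The Fisher sentence may cover responders.** SAP 7.5 promises the primary endpoints, lists Schirmer I and names a test for categorical variables. A reader might infer from the table list that the responder endpoint was deliberately left out by subgroup; the text does not support that. The supportable point is that text and table list disagree. Even on the generous reading, the output is percentages and a p-value, not a treatment difference with a CI.
4. **The 15% gate is prespecified in the protocol.** A reader might infer that level-specific results for region and Sjögren's type should always be shown. The gate stands in protocol 9.4.6, and the interaction tables themselves are produced whatever they show, so this point gives no reason to change it.

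**Conclusion.** The point holds as a reporting weakness, not as a flaw in the confirmatory analysis. For the four main subgroups the SAP presents neither an interaction nor a level-specific treatment difference with CI, while planning within-level tests. Under a uniform effect at the design values, those tests disagree between age halves in about 43% of trials for SANDE and about 40-45% for responders. The age figures rest only on document values. The 57% and 70% for SANDE at 75/25 and 85/15 rest on assumed level shares, and the pooling of small levels foreseen at the blind data review would alter them. All figures assume the same true effect in both levels. Separately, the promise to analyse the primary endpoints by subgroup and the Schirmer tables listed in SAP 15.1 must be reconciled.

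**What to change.** In SAP 7.5, for age class, race, ethnicity and gender, and for both co-primaries:

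- report the treatment effect with 95% CI in each level: the difference in the week-4 responder proportion (above 10 mm/5 min), and the adjusted difference in week-12 SANDE change;
- report one treatment-by-subgroup interaction estimate with its CI;
- drop the within-level p-values;
- add the matching responder and SANDE tables to SAP 15.1, so that the list agrees with the text.

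Leave the protocol's 15% gate for the further subgroups as it is.

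The cost is SAP wording and a few tables. No data collection changes, and it can be done before unblinding. The downside is imprecision. With a SANDE interaction SE of about 8.4 points for even halves, the interaction estimate has a 95% interval of roughly ±16.5 points (1.96 × 8.43) and should be read as a consistency check. Responder counts will also be small: at a 5% vehicle rate, an age half of about 22.5 vehicle patients yields about one responder (0.05 × 22.5 = 1.1), so the interval method should tolerate sparse cells. Sparse levels can use the pooling that SAP 7.5 already foresees.

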8.6 Prior and concomitant medications

A medication is defined:

- “Prior medication” if taken and stopped prior to first dose of study treatment.
- “Concomitant medication” if taken after the first dose of study treatment.

according to the available parts of the medication dates (see Table 7). In case of missing information not directly allowing allocation to either of the two above categories of medications, the medication will be considered as concomitant.

Prior and/or concomitant medications will be coded using World Health Organization Drug Dictionary and reported in separate tabulations. Frequency distributions and percentages will be summarized by treatment, type (Ophthalmic and Non-Ophthalmic), by Anatomical Main Group (1st level of the Anatomical Therapeutic Chemical (ATC) classification), Chemical Subgroup (4th level of the ATC classification) and Preferred Name.

Subjects taking more than one medication classified in the same category will be counted only once.

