12.5 Partial date conventions

Table 6: Algorithm for Treatment Emergence of Adverse Events

AE START DATE	AE STOP DATE	RULE for TEAE definition	RULE for “Treatment”/“Follow-up” study period definition for TEAE summaries
Known	Known, Partial or Missing	If AE start date < IMP start date, then not TEAE If AE start date \geq IMP start date, then TEAE	In case of Treatment Discontinuation: If start date \geq Date of last IMP intake, then Follow-up study period for TEAE occurrence. Otherwise, Treatment study period for TEAE occurrence. In case of NO Treatment Discontinuation: If start date \geq Date of “Day 21” visit, then Follow-up study period for TEAE occurrence. Otherwise, Treatment study period for TEAE occurrence.
Partial, but known components show that it cannot be on or after IMP start date	Known, Partial or Missing	Not TEAE	Not applicable

AE START DATE	AE STOP DATE	RULE for TEAE definition	RULE for "Treatment"/"Follow-up" study period definition for TEAE summaries
Partial, could be on or after IMP start date	Known	If AE stop date < IMP start date, then not TEAE If AE stop date \geq IMP start date, then TEAE	If TEAE, then Treatment study period for TEAE occurrence.
	Partial	Impute stop date as latest possible date (i.e. last day of month if day unknown or 31st December if day and month are unknown), then: If AE stop date < IMP start date, then not TEAE If AE stop date \geq IMP start date, then TEAE	
	Missing	Assumed TEAE	
Missing	Known	If AE stop date < IMP start date, then not TEAE If AE stop date \geq IMP start date, then TEAE	If TEAE, then Treatment study period for TEAE occurrence.
	Partial	Impute AE stop date as latest possible date (i.e. last day of month if day unknown or 31st December if day and month are unknown), then: If AE stop date < IMP start date, then not TEAE If AE stop date \geq IMP start date, then TEAE	
	Missing	Assumed TEAE	

NOTE: Assignment to "Treatment" or "Follow-up" study period is applicable only for TEAEs.

Table 7: Algorithm for Prior/Concomitant medications

MEDICATION START DATE	MEDICATION STOP DATE	RULE for prior or concomitant categorization
Known	Known	
If medication stop date < date of first dose of IMP, assign as prior
 
If medication stop date \geq date of first dose of IMP, assign as concomitant

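### The concomitant-medication subgroup admits medicines started after the first dose, with no end date, so its interaction test and subgroup effects can be biased

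*SAP*

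**What the plan says.** SAP 7.5 contains two separate subgroup lists. The first is introduced by "Subgroup analyses of primary and secondary endpoints will be performed on the following subgroups of baseline characteristics" and holds age class, race, ethnicity and gender. The second is introduced by "Variables that may be evaluated after test for interaction are" and holds region, type of Sjögren's syndrome, medical history and "Concomitant medication". A variable in the second list proceeds when its interaction with treatment is "statistically significant at 15% nominal level in at least one regression model, then subgroup analysis will be performed". Protocol 9.4.6 also keeps two lists and puts concomitant medication in the second: "Statistical tests for interaction (between subgroup variable and treatment arm) will be performed before investigate further subgroups".

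SAP 8.6 calls a medicine concomitant "if taken after the first dose of study treatment". Where missing information prevents allocation, "the medication will be considered as concomitant". Table 7 (SAP 12.5) turns this into a rule on the stop date alone: when the stop date falls on or after the first dose, the instruction ends "date of first dose of IMP, assign as concomitant". The start date plays no part and there is no latest date. Neither document names the classes or levels of this subgroup.

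The analysis is scheduled. SAP 15.1 lists treatment-by-concomitant-medication models for both co-primary endpoints (Tables 14.2.6.1.4 and 14.2.6.2.4), and a repeat of the subgroup tables if the interaction is significant.

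**The concern.** A subgroup analysis keeps the protection of randomisation only if membership is settled before treatment can act. Here part of the membership is settled afterwards. Systemic treatment may change at any time during the study (SAP 3.3), and other topical treatments are allowed after week 12 until week 24. A patient with a poor week-12 SANDE score may start such a treatment and so become a user in the analysis of that same week-12 score. SAP 6.2 and 7.9 replace the protocol's week-12 lock with a single lock at the end of the study, so these later medicines will be in the data when the subgroup is formed.

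If treatment changes who starts a medicine, and starting is related to outcome, users on the two arms are not comparable, and neither are non-users. The 15% interaction test gives no protection, because it uses the same variable. What is at stake is a misleading statement about which patients appear to benefit.

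**Working it through.** **1. The plan's own figures.** The SAP gives no figure for this subgroup. Its power statement (SAP 5) reproduces. With 45 per arm and one-sided 0.025, 35% against 5% gives 95.8% (pooled two-proportion formula), and 15 points with SD 20 gives 94.0% (noncentral t). The product is 0.958 × 0.940 = 0.90. None of this depends on the subgroup definition.

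**2. What the rule captures.**

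| Medicine | Table 7 class | Can treatment or outcome affect it? |
|---|---|---|
| Started before, stopped before first dose | Prior | No |
| Started before, ongoing at first dose | Concomitant | Not its presence at baseline |
| Started after first dose, up to week 12 | Concomitant | Yes |
| Started in weeks 13 to 24 | Concomitant | Yes, including by the week-12 score |
| Stop date missing | Concomitant | Unknown |

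**3. Possible size (assumed model).** From SAP 5: SANDE effect 15, SD 20. Assumptions: every patient has the same true effect. Improvement is Y = 15T + 20U, with T = 1 on cenegermin and 0 on vehicle. A new medicine is started when S > 0, where S = −ρ(Y − 7.5)/20 + √(1 − ρ²)E. U and E are independent standard normals, and ρ is the within-arm strength of the link between poor outcome and starting. To mimic Table 7, a random 40% of patients are also on a medicine ongoing at baseline.

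Within arm, S has mean +0.375ρ on vehicle and −0.375ρ on cenegermin (7.5/20 = 0.375), with SD 1. With m = 0.375ρ, the mean of non-users rises by 20ρφ(m)/Φ(−m) on vehicle and by 20ρφ(m)/Φ(m) on cenegermin.

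At ρ = 0.7, m = 0.2625 and φ(m) = 0.3854:
- vehicle: 14 × 0.3854/0.3965 = 13.61
- cenegermin: 14 × 0.3854/0.6035 = 8.94
- apparent effect in non-users: 15 + 8.94 − 13.61 = 10.33

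A simulation of 2,000,000 patients per setting gives:

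| ρ | Users (Table 7 mixture) | Non-users |
|---|---|---|
| 0 | 15.00 | 14.99 |
| 0.2 | 14.95 | 14.62 |
| 0.3 | 14.89 | 14.22 |
| 0.5 | 14.56 | 12.66 |
| 0.7 | 14.14 | 10.33 |

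At ρ = 0.7 the two levels differ by 14.14 − 10.33 = 3.81 points although no true interaction exists. If the subgroup is instead medication ongoing at baseline, both levels stay between 14.97 and 15.06 at every ρ.

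**4. How often the 15% test passes by chance.** With no true interaction, and treating the tests as independent (an approximation, since they share patients), one variable passes in at least one of two models with probability 1 − 0.85² = 27.8%. At least one of four variables passes with probability 1 − 0.85⁸ = 72.7%. The test is therefore easily passed even without the bias in step 3.

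**The case against.** Four points count on the other side.

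- A reader might infer that the SAP calls concomitant medication a baseline characteristic and so contradicts itself. It does not: that phrase introduces only the age, race, ethnicity and gender list.
- A reader might infer that the subgroup is formed wholly after randomisation. It is not: Table 7 also captures medicines started earlier and still ongoing, and patients may continue systemic therapy for their autoimmune disease.
- Up to week 12, eye treatment other than study drug is limited to sponsor-supplied artificial tears (Protocol 6.2), whose use is summarised separately (SAP 9.3). The obvious route, topical rescue for poor response, is largely closed before both co-primary assessments. This narrows the mechanism but does not remove it. Systemic changes are allowed throughout, and topical medicines started after week 12 still determine membership because the rule has no end date.
- The analyses are conditional and descriptive. They carry no alpha and are outside the key secondary hierarchy. This stands, and it sets the severity.

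The upper end of the range also needs strong selection. At correlations of 0.2 to 0.3 the distortion is below one point of 15. A simpler scenario, in which exactly the worst 20% on vehicle and the worst 10% on cenegermin start a medicine, shifts non-users by 7.0 and 3.9 points and gives 15 − (7.0 − 3.9) = 11.9. It assumes that outcome alone decides use, so it is close to a worst case.

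**Conclusion.** The point holds as a minor one. As written, the subgroup combines a legitimate baseline component with a component that treatment or outcome can influence, and nothing in either document separates them. The interaction test and the subgroup effects can therefore be biased.

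It would go too far to say that they are biased. Bias needs medication use after dosing to depend on treatment and to relate to outcome, and the documents do not show how strongly either applies. The range of about 15.0 to 10.3 in non-users rests on the assumed model: a uniform effect of 15, SD 20, correlations from 0 to 0.7, roughly half of patients starting a medicine, and 40% on one at baseline. It is an illustration of size, not a prediction. The co-primary analyses, type I error, sample size and power are unaffected.

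**What to change.** In SAP 7.5, define this subgroup as medication started before the first IMP dose and not stopped before it. Fix the medication classes and their levels at the blind data review, where SAP 7.5 already places decisions on pooling subgroup levels. Add a convention for missing or partial start dates, because Table 7 imputes stop dates only. Report medication started after the first dose descriptively by arm, and do not use it as an interaction or subgroup variable. Table 7 can stay as it is for the general medication tables.

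The cost is a few lines of SAP text and one derivation rule, agreed before unblinding. Protocol 5.6 already collects start and discontinuation dates, so no new data are needed. Protocol 9.4.6 contains no post-dose definition and leaves statistical details to the SAP, so the SAP change is sufficient.
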